#### **Description of AEs requiring additional data collection (via specific event form) and AESIs**

##### **AESIs**

An AESI is an event, which in the evaluation of safety, has a special focus due to requirements from regulatory authorities.

##### **In this trial, the following AEs fulfil the AESI criteria:**

Thromboembolic events including but not limited to,

- disseminated intravascular coagulation (DIC) (A),
- thrombotic microangiopathy (TMA)(B)
- myocardial infarction (C),
- pulmonary embolism (D),
- stroke (E),
- deep vein thrombosis (F),
- other clinically significant thromboembolic events (G) and peripheral artery occlusion (see below H), see definitions below

In case of suspicion of thromboembolic events, further investigations and appropriate medical treatment should be initiated. Additionally, it is encouraged to perform a COVID-19 test in the case of a suspected thromboembolic event. If a thromboembolic event is diagnosed, COVID-19 testing must be performed.

##### **A) Definition of disseminated intravascular coagulation (DIC), as defined below:**

The definition of DIC in this trial should be made according to the International Society on Thrombosis and Haemostasis (ISTH) criteria. Thus, a DIC diagnosis may be based on clinical signs and symptoms of a bleeding tendency or thrombotic tendency, organ dysfunction and the laboratory parameters criteria as listed below:

- Platelet count ( $>100 \times 10^9/L = 0, <100 \times 10^9/L = 1, <50 \times 10^9/L = 2$ )
- Elevated D-dimer (no increase = 0, moderate increase = 2, strong increase = 3)
- Prolonged PT ( $<3 s = 0, >3$  but  $<6 s = 1, >6 s = 2$ )
- Fibrinogen level ( $>1 g/L = 0, <1 g/L = 1$ )
- Calculate score:  $\geq 5$  compatible with overt DIC

**B) Definition of thrombotic microangiopathy, as defined below:**

Thrombotic microangiopathies (TMA) are a group of disorders characterized by microangiopathic hemolytic anemia, thrombocytopenia and microthrombi leading to ischemic tissue injury that can affect e.g. the kidneys and the central nervous system.

TMA is a clinicopathologic diagnosis. The constellation of thrombocytopenia, anemia and red blood cell fragmentation (i.e. schistocytes) on the blood film is consistent with a diagnosis of TMA. The finding of concomitant anemia and thrombocytopenia should prompt a request for a peripheral blood film to look for red blood cell fragmentation.

If TMA is suspected the following laboratory assessment workup is suggested: standard hematology, hemolytic parameters (reticulocytes, hemoglobin, bilirubin, LDH, haptoglobin), Direct Anti-Globulin (DAT) test (also referred to as Coombs test), peripheral blood smear to look for schistocytes, creatinine, ADAMTS13 Antigen and ADAMTS13 Antibody.

**C) Myocardial infarction is defined according to the “Third Universal Definition of Myocardial Infarction”**

Criteria for acute myocardial infarction - The term acute myocardial infarction (MI) should be used when there is evidence of myocardial necrosis in a clinical setting consistent with acute myocardial ischemia. Under these conditions any one of the following criteria meets the diagnosis for MI:

- Detection of a rise and/or fall of cardiac biomarker values [preferably cardiac troponin (cTn)] with at least one value above the 99th percentile upper reference limit (URL) and with at least one of the following:
  - Symptoms of ischemia
  - New or presumed new significant ST-segment-T wave (ST-T) changes or new left bundle branch block (LBBB)
  - Development of pathological Q waves in the ECG
  - Imaging evidence of new loss of viable myocardium or new regional wall motion abnormality
  - Identification of an intracoronary thrombus by angiography or autopsy

Criteria for prior myocardial infarction - Any one of the following criteria meets the diagnosis for prior MI:

- Pathological Q waves with or without symptoms in the absence of non-ischemic causes.
- Imaging evidence of a region of loss of viable myocardium that is thinned and fails to contract, in the absence of a non-ischemic cause.
- Pathological findings of a prior MI.

Recurrent myocardial infarction - Incident MI is defined as the individual's first MI. When features of MI occur in the first 28 days after an incident event, this is not counted as a new event for epidemiological purposes. If characteristics of MI occur after 28 days following an incident MI, it is considered to be a recurrent MI.

**D) Definition of pulmonary embolism:**

The “Clinical Practice Guideline from the American Academy of Family Physicians and the American College of Physicians” on diagnosis of venous thromboembolism recommends diagnostic imaging studies for patients with intermediate or high pre-test probability of pulmonary embolism.

Accordingly, the definition of pulmonary embolism is the following: obstruction of a pulmonary artery or one of its branches, most frequently by detached fragments of thrombus from a leg or pelvic vein, diagnosed by at least one of the following:

- Positive findings in ventilation/perfusion scan
- Positive findings in a spiral (helical) computerised tomography (CT) or angiography
- Positive findings in a magnetic resonance imaging (MRI)
- Positive findings in a pulmonary angiography

**E) Definition of stroke:**

The definition of central nervous infarction is according to the American Heart Association/American Stroke Association Expert Consensus Document: “An Updated Definition of Stroke for the 21st Century”.

Accordingly, the term “stroke” should be broadly used to include all of the following:

Definition of central nervous system (CNS) infarction: CNS infarction is brain, spinal cord or retinal cell death attributable to ischemia, based on:

pathological, imaging or other objective evidence of cerebral, spinal cord or retinal focal ischemic injury in a defined vascular distribution or clinical evidence of cerebral, spinal cord or retinal focal ischemic injury based on symptoms persisting 24 hours or until death, and other aetiologies excluded

Note: CNS infarction includes haemorrhagic infarctions, types I and II; see “Haemorrhagic Infarction”.

**Definition of ischemic stroke:** An episode of neurological dysfunction caused by focal cerebral, spinal or retinal infarction. Note: Evidence of CNS infarction is defined above.

**Definition of silent CNS infarction:** Imaging or neuropathological evidence of CNS infarction, without a history of acute neurological dysfunction attributable to the lesion.

**Definition of intracerebral haemorrhage:** A focal collection of blood within the brain parenchyma or ventricular system that is not caused by trauma. Note: Intracerebral haemorrhage includes parenchymal haemorrhages after CNS infarction, types I and II - see “Haemorrhagic Infarction”.

**Definition of stroke caused by intracerebral haemorrhage:** Rapidly developing clinical signs of neurological dysfunction attributable to a focal collection of blood within the brain parenchyma or ventricular system that is not caused by trauma.

**Definition of silent cerebral haemorrhage:** A focal collection of chronic blood products within the brain parenchyma, subarachnoid space or ventricular system on neuroimaging or neuropathological examination that is not caused by trauma and without a history of acute neurological dysfunction attributable to the lesion.

**Definition of subarachnoid haemorrhage:** Bleeding into the subarachnoid space (the space between the arachnoid membrane and the pia mater of the brain or spinal cord).

**Definition of stroke caused by subarachnoid haemorrhage:** Rapidly developing signs of neurological dysfunction and/or headache because of bleeding into the subarachnoid space (the space between the arachnoid membrane and the pia mater of the brain or spinal cord), which is not caused by trauma.

**Definition of stroke caused by cerebral venous thrombosis:** Infarction or haemorrhage in the brain, spinal cord or retina because of thrombosis of a cerebral venous structure. Symptoms or signs caused by reversible edema without infarction or haemorrhage do not qualify as stroke.

**Definition of stroke, not otherwise specified:** An episode of acute neurological dysfunction presumed to be caused by ischemia or haemorrhage, persisting  $\geq 24$  hours or until death, but without sufficient evidence to be classified as one of the above.

**Definition of a Transient Ischemic Attack:** The definition of Transient Ischemic Attack is according to the American Heart Association/American Stroke Association. A Transient ischemic attack (TIA) is a transient episode of neurological dysfunction caused by focal brain, spinal cord or retinal ischemia, without acute infarction.

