| Safety                                                   |                                                                                                                                                                                                                                                                                                                                                                                                                                                                                                                                                                                                                                         |       |
| Number of thromboembolic events                                 | 
On demand (arm 1 main part)
 
 
From randomisation to on demand treatment up until start of concizumab treatmentd
 
 
Concizumab (arms 2-4)
 
 
Before the pausec: From start of concizumab treatment (week 0b) up until 7 weeks after the treatment was paused
 
 
as well as
 
 
After the pausec: From start of concizumab treatment (week 0a) up until the primary analysis cut-off (at least 32 weeks)
 
 | Count |

| Endpoint title                            | Time frame                                                                                                                                                                                                                                                                                                                                                                                                                                                                                                                                                                                                                                                                                                                                                                   | Unit  |

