### Treatment arms 1 and 2:

Approximately 51 patients (27 HAwI and 24 HBwI), previously treated on-demand, will be randomised 1:2 to no prophylaxis versus concizumab prophylaxis. Patients will be stratified by the haemophilia type and the bleeding frequency.

**Patients randomised to arm 1 before the pause** were instructed to continue their on demand treatment and report data until trial restart. It is expected that all of these patients will have completed at least 24 weeks of on demand treatment when restarting the trials. Upon completion of the main part, the arm 1 patients will start the new concizumab dosing regimen (see Section [5.2.1](#)) and receive up to 136 weeks of concizumab PPX in the extension part of the trial.

**Patients randomised to arm 2 before the pause** have discontinued their concizumab treatment and received available standard of care during the pause. Upon restart, patients who do not fulfil any discontinuation criteria (see Section [8](#)) will receive the new concizumab dosing regimen from visit 2a (described in Section [5.2.1](#)).

**New patients eligible for arms 1 and 2** will be recruited to fulfill the protocol target numbers. New patients eligible for arms 1 and 2 will be randomised as outlined in Section [7.2](#).

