**Table 10 Definition of bleeding episode severity**

| Category             | Definition                                                                                                                                                                                                                                                                                                                                                            |
|----------------------|-----------------------------------------------------------------------------------------------------------------------------------------------------------------------------------------------------------------------------------------------------------------------------------------------------------------------------------------------------------------------|
| Mild/Moderate | Examples: uncomplicated musculoskeletal bleeds (joint, muscular bleeds without compartment syndrome), mucosal- or subcutaneous bleeds
Mild/moderate bleeds may occur in other anatomical locations                                                                                                                                                                 |
| Severe        | Examples: intracranial, retroperitoneal, iliopsoas and internal neck bleeds; muscle bleeds with compartment syndrome; bleeds associated with a significant decrease in the haemoglobin level ( $>3\text{g/dl}$ )
Severe bleeds may occur in other anatomical locations
Bleeding episodes that require hospitalisation
All life-threatening bleeding episodes |

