## **Bleeding episodes in relation to AE/SAEs**

Because bleeding episodes are associated with the disease under study, they will not be reported according to the standard process for reporting of AEs/SAEs, even though the bleeding episode (event) may meet the definition of an AE/SAE unless they meet the criteria as specified below.

Note: The event must be recorded and reported as an AE/SAE if one of the following applies:

- The event is, in the investigator's opinion, of greater intensity, frequency, or duration than expected for the individual patient.
- The investigator considers that there is a reasonable possibility that the event was related to treatment with the investigational product.
- The event was life-threatening or resulted in death.

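### As written, a primary brain haemorrhage reported as an AESI would be counted as a thromboembolic event in the week-56 safety tables

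*Protocol*

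**What the plan says.** The AESI criteria in protocol section 9.3.1.1 and Appendix 5 open with "Thromboembolic events including but not limited to". They name stroke as one item, and Appendix 5 refers it to definition E.

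Definition E says the term "should be broadly used to include all of the following". The entries then cover CNS infarction, ischaemic stroke and silent infarction, but also intracerebral haemorrhage, silent cerebral haemorrhage and subarachnoid haemorrhage. A note adds that "Intracerebral haemorrhage includes parenchymal haemorrhages after CNS infarction, types I and II", so bleeding after an infarct is one subset of that entry and not a condition for it. The residual category also admits bleeding: "An episode of acute neurological dysfunction presumed to be caused by ischemia or haemorrhage".

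Bleeds have a rule of their own. Under section 9.3.6 they are disease-related events, and "they will not be reported according to the standard process for reporting of AEs/SAEs" unless one of three criteria applies: worse than expected for the patient, possibly related to the product, or life-threatening or fatal. The severe category in Table 10 begins "Examples: intracranial, retroperitoneal, iliopsoas and internal neck bleeds".

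"Number of thromboembolic events" is a supportive secondary endpoint in protocol section 4.3.2.2 and an assessment in Appendix 2 of the week-56 SAP. SAP section 5.6.2 defines and categorises thromboembolic events as AESIs. SAP Table 1 presents them on the safety analysis set in two data sets, with and without time on the initial dosing regimen. SAP section 2 states that nothing is tested at week 56.

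**The concern.** The development programme was paused because of thromboembolic events, and this count describes that risk under the new regimen. The patients have a bleeding disorder, so a CNS haemorrhage is a plausible event in either condition. If it is tabulated as thromboembolic, a bleed in the on-demand period of arm 1 gives the comparator a thrombosis it did not have, and a bleed on concizumab adds to the apparent thrombotic risk. The same event would also appear as a severe bleed, so it would be read once as failed haemostasis and once as excess coagulation. The direction of the distortion is not fixed in advance.

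**Working it through.** **Text chain.**

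1. Is stroke a thromboembolic AESI? Yes: it is listed in section 9.3.1.1 and in Appendix 5.
2. Does definition E reach primary haemorrhage? Yes. The intracerebral and silent entries exclude trauma only, and none of the haemorrhage entries requires an infarct or a thrombus. By contrast, the eligibility footnote on thromboembolic disease (section 6.2) names cerebral infarction and thrombosis and does not mention haemorrhage.
3. Can such a bleed become an AE/SAE? Yes, if it meets one of the three criteria in sections 9.2.3 and 9.3.6. A symptomatic intracranial bleed could readily do so. A silent one is less likely to be found, since it needs imaging or pathology that the flowchart does not schedule.
4. Does the week-56 SAP remove it? Section 5.6.2 gives no exclusion. Its MedDRA search precedes the thromboembolic sentence and refers to hypersensitivity reactions, medication errors and injection site reactions. No adjudication step was found in either document.

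**Scale of one event.** The documents give no intracranial bleed rate and no expected thromboembolic rate to reproduce, so this shows scale only and is not a forecast.

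Inputs: arm 1 = 9 + 8 = 17; arm 2 = 18 + 16 = 34; arm 3 up to 15 + 10 = 25; arm 4 = 60 (protocol Table 2). Arms 2-4 = 34 + 25 + 60 = 119. Weeks per year = 365.25/7 = 52.18. Patient-years (PY) = patients x weeks / 52.18. Rate = 100 / PY for one event. Limits are exact Poisson: 0.0253 to 5.572 for one event, upper limit 3.689 for none.

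With 56 weeks each and no dropout:

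- Arm 2: 34 x 56/52.18 = 36.5 PY. One event is 2.7 per 100 PY (0.1 to 15.3); none is 0 (0 to 10.1).
- Arms 2-4: 119 x 56/52.18 = 127.7 PY. One event is 0.8 (0.0 to 4.4); none is 0 (0 to 2.9).

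Two departures from that assumption pull in opposite directions:

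- *Dropout.* If 17% leave half-way (section 10.1 expects less than 17% in arms 1 and 2; extending this to arms 3 and 4 is an assumption), PY shrink by 1 - 0.17/2 = 0.915, to 33.4 and 116.9. The rates become 3.0 and 0.9.
- *Longer follow-up.* Time runs to the cut-off, which is the date when all patients in arms 2-4 have completed visit 13a or permanently discontinued treatment. Early starters therefore contribute more than 56 weeks. At an assumed mean of 80 weeks, PY are 34 x 80/52.18 = 52.1 and 119 x 80/52.18 = 182.4, and the rates are about 1.9 and 0.55.

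Arm 1, on-demand period: 17 x 24/52.18 = 7.8 PY, or 12.8 per 100 PY for one event. This is an upper bound apart from dropout, because patients randomised to arm 1 before the pause "were instructed to continue their on demand treatment and report data until trial restart". Assumed means of 36 and 52 weeks give 11.7 and 16.9 PY, or 8.5 and 5.9.

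**Which zero.** The comparison with no events fits the data set without the initial regimen. The full on-treatment set includes exposure before the pause, and protocol section 3.2 reports that one patient in this trial had already had a serious thromboembolic event. That set may therefore not start from zero.

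**The case against.** The case on the other side has four parts.

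- *The count does not follow automatically.* The AESI heading speaks of thromboembolic events, item G adds other clinically significant ones, and definition E opens by citing a source for CNS infarction. Section 9.3.6 says that a qualifying bleed is reported as an AE/SAE and does not mention AESI. A site could report a life-threatening haemorrhage only as a serious bleed. This stands. A reader might infer that every primary CNS bleed is bound to be counted, but the documents do not support that; the outcome depends on the event being reported as an AESI.
- *Other documents may settle it.* The SAP introduction places derivations in the analysis data reviewer's guide and table specifications in the mock tables, and refers the main-part analyses to the SAP for the primary cut-off. None was available. This stands, so it should not be inferred that the supportive secondary endpoint at the primary cut-off has the same problem.
- *Broad capture is prudent for a procoagulant.* The list follows a published consensus definition, cerebral venous thrombosis can present as haemorrhage, and section 3.3 notes that excessive coagulation activation might cause bleeding through factor consumption. This is a good reason to keep reporting broad. It is not a reason to tabulate primary haemorrhage under a thromboembolic title.
- *A careful reader could find the event.* MedDRA coding and the CNS location rows in SAP section 5.5.1 would reveal it. That is true, and it limits the consequence, but those rows do not take the event out of the headline count.

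**Conclusion.** The point holds, and it is minor. A stated definition, and not merely missing detail, allows a primary CNS bleed to enter a count titled thromboembolic. This requires that the bleed meets an AE/SAE criterion, is reported as an AESI, falls in the on-treatment period, and is not removed by a rule in the documents that were not available.

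The size is one event in a very small count. Apart from dropout, 2.7 per 100 PY for arm 2 and 0.8 for arms 2-4 are upper figures. They rest on the planned enrolment being reached, and the comparison with zero applies only to the data set without the initial regimen. No expected number of such events can be given from the documents.

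A reader might also infer that the trial's confirmatory conclusions are affected. They are not: the SAP introduction bases those on the primary analysis cut-off, and the week-56 analyses are descriptive.

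**What to change.** Leave AESI reporting by sites as broad as it is, and put a counting rule in SAP section 5.6.2:

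- From definition E, count as thromboembolic only CNS infarction (with haemorrhagic infarction, counted once), ischaemic stroke, silent CNS infarction, stroke caused by cerebral venous thrombosis, and transient ischaemic attack.
- Count stroke not otherwise specified as thromboembolic unless imaging shows primary haemorrhage.
- Show primary intracerebral, silent cerebral and subarachnoid haemorrhages that meet an AE/SAE criterion on a separate safety row, by arm and for all concizumab patients together.
- Show the combined total of thromboembolic and haemorrhagic AESIs.

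If the SAP for the primary cut-off, the reviewer's guide or the mock tables already contain such a rule, repeat it in the week-56 SAP.

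The cost is a few lines of text and two table rows. No new data are needed: AESIs already have an AE form and a safety information form, and the split can use the diagnosis that the investigator records under Appendix 5. The downside is that the thromboembolic count may be slightly lower, and narrowing it in an open-label trial could look selective. The combined total discloses exactly what was moved.

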#### **F) Definition of deep vein thrombosis:**

The “Clinical Practice Guideline from the American Academy of Family Physicians and the American College of Physicians” on diagnosis of venous thromboembolism recommends ultrasound scanning for patients with intermediate or high pre-test probability of deep vein thrombosis (DVT) in the lower extremities. Accordingly, venous thrombosis should be demonstrated by compression ultrasound, duplex ultrasound, colour Doppler imaging or venography (phlebography).

